Apretude is given first as two initiation injections administered one month apart, and then every two months thereafter. Individuals can either start their treatment with Apretude, known as direct to injection (DTI), or take oral cabotegravir (Vocabria) for four weeks as an optional oral lead-in (OLI) to assess how well they tolerate the drug. Oral cabotegravir may also be used as oral PrEP in individuals who miss planned dosing with CAB LA injection.²

Efficacy assessment from pivotal studies (HPTN 083 and HPTN 084), designed to assess the safety and efficacy of CAB PrEP when compared to the active comparator daily oral TDF/FTC for HIV PrEP in the most key affected populations globally (i.e., MSM and TGW [enrolled in HPTN 083] and cisgender women [enrolled in HPTN 084]) demonstrated superiority.^{3,4}

In 083, CAB PrEP demonstrated superior efficacy among MSM and TGW when compared to daily oral TDF/FTC (HR 0.34; 95% CI 0.18 to 0.62, two-sided p=0.0005), with an approximate 66% reduction in the rate of incident infections. There were 39 HIV

incident infections in the TDF/FTC group (incidence rate 1.22/100 PY) and 13 incident infections occurred in the CAB group (incidence rate 0.40/100 PY).³

In 084, CAB PrEP demonstrated superior efficacy among cisgender women when compared to daily oral TDF/FTC (HR of 0.11 (95% CI 0.04 to 0.31), p<0.0001) demonstrating an 89% reduction in the rate of incident infections for CAB. There were 36 HIV incident infections in the TDF/FTC group (incidence rate 1.85/100 PY) and 4 HIV incident infections occurred in the CAB group (incidence rate 0.20/100 PY).⁴

CAB tablets are indicated for short term PrEP to reduce the risk of sexually acquired HIV-1 infection in at-risk individuals weighing at least 35 kg. The tablets may be used as:

- OLI for one month to assess tolerability of CAB prior to administration of the injection.
- Oral PrEP in individuals who miss planned dosing with CAB LA injection.

CAB LA injections are indicated for PrEP to reduce the risk of sexually acquired HIV-1 infection in at-risk individuals weighing at least 35 kg.

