7.2. Study Population and Setting

7.2.1. Study Setting

Potential investigational sites within the NEAT-ID Network across Europe will be contacted for feasibility and resistance testing practices as part of their SoC. A formal feasibility assessment questionnaire will be conducted after the protocol is finalized and approved and will be used to determine sites' eligibility to participate in the study. This formal feasibility assessment will include assessing site's infrastructure to participate in research studies, number of any PrEP prescriptions in the previous year, availability of resistance testing, and HIV testing practices per local standard of care practices. Followup period will start from the date of the first participant enrolled in the study and will end five years after the date of first enrolment.

Participant data will be collected via extraction from electronic medical records (i.e., source data) by appropriately trained and authorized member(s) of the study team who must be identified and authorized in writing by the Principal Investigator (PI). A delegation of responsibility log will be maintained accordingly. In order to maintain confidentiality, the participants will be identified only by study number.

All data will be entered directly into the electronic data capture (EDC) by the sites and will be checked for completeness every 6 months by the data coordinating center. NEAT-ID's management team will store the data on a secure network drive with access to authorized personnel of the data management team only, maintained on a log of authorized personnel by the data coordinating center.

NEAT-ID team will perform site management activities to assess protocol issues, consent, data quality and study management quality performance.

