7.4.1. Study size

The study is not a hypothesis testing study, but it is designed to assess usage of CAB LA for PrEP in real world clinical settings. The overall number of participants in this cohort study will depend on the uptake of the CAB LA for PrEP and how widely it will be used across the NEAT-ID clinical sites.

The study aims to include a target of at least 500 participants initiating CAB LA for PrEP. There is no formal statistical hypothesis to be tested in these analyses. Table 1 below gives an indication of the likely precision of the estimates of the proportion with incident HIV, using Exact Clopper Pearson confidence limits under different scenarios.

Confidence Level	Sample Size (N)	CI Width	Incident HIV rate (%)	Lower Limit	Upper Limit
0.95	500	1.1824	0.25	0.0118	1.1942
0.95	500	1.5093	0.50	0.0832	1.5925
0.95	500	1.9926	1.00	0.3255	2.3181
0.95	500	2.3679	1.50	0.6283	2.9962
0.95	500	2.6841	2.00	0.9631	3.6472
0.95	500	2.9617	2.50	1.3185	4.2802
0.95	1000	0.7568	0.25	0.0416	0.7984
0.95	1000	1.0004	0.50	0.1625	1.1629
0.95	1000	1.3507	1.00	0.4806	1.8313
0.95	1000	1.6201	1.50	0.8419	2.4620
0.95	1000	1.8462	2.00	1.2258	3.0720
0.95	1000	2.0442	2.50	1.6243	3.6685
0.95	2000	0.5012	0.25	0.0812	0.5824
0.95	2000	0.6776	0.50	0.2400	0.9176
0.95	2000	0.9283	1.00	0.6119	1.5402

Table 1: Precision estimates

CONFIDENTIAL

CTMS Project Number: 221935 Final Protocol

				-	
0.95	2000	1.1202	1.50	1.0143	2.1345
0.95	2000	1.2810	2.00	1.4326	2.7136
0.95	2000	1.4217	2.50	1.8611	3.2828

Table 2 below shows the precision estimates for regimen discontinuation rates varying from 2.5% to 20% for a sample of 500 individuals.

Confidence Level	Sample Size (N)	CI Width	Discontinuation rate	Lower Limit	Upper Limit
0.95	500	0.0296	0.025	0.0132	0.0428
0.95	500	0.0403	0.050	0.0326	0.0729
0.95	500	0.0546	0.100	0.0751	0.1297
0.95	500	0.0646	0.150	0.1198	0.1844
0.95	500	0.0720	0.200	0.1658	0.2378

 Table 2. Precision estimates by discontinuation rate

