7.6. Data analysis

7.6.1. Essential analysis

Specific analytic methods are shown for each study objective. All CAB LA PrEP users will be followed for at least 3 years (36 months). All individuals with incident HIV acquisition will be followed through the end of the follow-up period. Participants discontinuing CAB LA PrEP will be monitored through the end of the follow-up period for HIV acquisition and, in the case of HIV acquisition, will be monitored for ART effectiveness and potential emergence of resistance.

In the event of a delay of ART initiation post HIV diagnosis, the study team will strive to follow the individual through the end of the follow-up period. Interim results will be generated at 12, 24, 36, 48 months since study initiation and final results will be generated at 60 months since study initiation.

Analysis for Objective 1 (Description of CAB for PrEP Usage pattern)

For individuals initiating CAB for PrEP, baseline demographics (age, sex, gender, ethnic origin (where available), BMI, geographic region), history of previous PrEP use and use of OLI prior to initiating injections will be described. Comorbidities, STIs, risk factors for HIV acquisition (e.g. HIV status of sexual partner, multiple sexual partners), will be reported as frequencies at baseline and at 6, 12, 24, 36, and >36 months of follow-up as available. Proportion of individuals using oral PrEP to cover planned, delayed or missed CAB LA injections will also be provided. Frequency of testing for HIV once initiated CAB for PrEP will be evaluated, and timing of HIV testing relative to injection dates will be assessed.

Prevalent HIV is defined as any undiagnosed HIV at the time of PrEP initiation and will be defined as positive HIV antigen/antibody test and/or positive viral load from sample collected at the time of initiation (first prescription of CAB oral lead and, separately, first CAB LA PrEP injection). Note the test result may be reported within 4-6 weeks after the sample was collected. Prevalent HIV will be reported at baseline while on CAB OLI and while on CAB LA. Also, prevalent HIV will be reported for those who received CAB OLI and separately for those with direct to injection (DTI) strategy. Incident HIV is any new HIV diagnosis that occurs after the initiation of CAB PrEP, having confirmed HIV negative status using HIV RNA test, at the time of PrEP initiation. Incident HIV reporting is described in objective 3.

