Frequency of undiagnosed prevalent HIV at CAB PrEP initiation will be assessed as described for objective 1. The primary effectiveness measure for objective 3 is proportion of individuals with incident HIV diagnosis during OLI and separately during CAB LA PrEP and will be calculated at 6, 12, 24, 36 months and over the entire length of follow-up. The proportion of incident infections among those who start with OLI and those who go to DTI will also be reported separately along with the timing of diagnosis of incident HIV acquisition for the overall group, and separately for the OLI and DTI groups.

Adherence patterns and characteristics of individuals with incident HIV diagnosis will be compared with those without incident HIV diagnosis, using t-test for continuous variables (Wilcoxon rank sum test for not normally distributed variables) or chi-square test for categorical variables. Participant characteristics significantly impacting acquisition of HIV based on univariate analysis will be selected for multivariable analysis. Risk for HIV acquisition and characteristics affecting risk for HIV acquisition will be assessed using negative binomial model with log-link function with binary outcome (HIV diagnosis vs not) if feasible.

Time to HIV diagnosis will be defined as time from first CAB LA PrEP injection to the first HIV diagnosis using laboratory antigen/antibody test, confirmed by viral RNA test. Time to HIV diagnosis will be assessed using Kaplan-Meier curve. Differences in time to diagnosis will be assessed by sex, gender, ethnicity (where available), geographic region, and risk factors (e.g. STI, previous PrEP usage) related, adherence to current PrEP to HIV acquisition. Additionally, time to diagnosis will be shown for people who acquired the infection while prescribed oral CAB lead in (if applicable). Time to diagnosis in this group will be defined as time from first CAB oral prescription to the first positive HIV-1 antigen/antibody lab result, confirmed by viral RNA test.

If feasible, Cox proportional hazards models will be constructed to compare time to HIV diagnosis by subgroup adjusting for additional variables (e.g., sex, ethnicity, (where available) geographic region).

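### The Objective 3 chi-square comparison of people with and without incident HIV rests on about 3 to 6 expected cases, too few for its p-values to be reliable or to choose covariates

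*Protocol*

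**What the plan says.** Under the analysis for Objective 3, Protocol 7.6.1 compares adherence patterns and characteristics of people with an incident HIV diagnosis against those without, "using t-test for continuous variables (Wilcoxon rank sum test for not normally distributed variables) or chi-square test for categorical variables". No condition is attached to this comparison, and no exact test or small-cell rule is named. The next sentence gives the p-values a job: "Participant characteristics significantly impacting acquisition of HIV based on univariate analysis will be selected for multivariable analysis". The feasibility condition in that section is attached to the negative binomial and Cox models, not to the univariate tests.

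The case count follows from figures elsewhere in the protocol:
- Section 7.4.1 sets the size: "The study aims to include a target of at least 500 participants initiating CAB LA for PrEP".
- Section 7.6.1 promises at least 36 months of follow-up per person, and section 7.2.1 says that follow-up "will end five years after the date of first enrolment".
- Section 5.1 gives the rates on cabotegravir in the two pivotal trials: "13 incident infections occurred in the CAB group (incidence rate 0.40/100 PY") and "4 HIV incident infections occurred in the CAB group (incidence rate 0.20/100 PY").

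Section 7.4.1 also states that no formal hypothesis is tested. It gives the precision of the incident-HIV proportion "using Exact Clopper Pearson confidence limits under different scenarios".

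**The concern.** The chi-square test relies on a large-sample approximation that fails when expected counts are small. Here one group is a handful of people and the other is nearly the whole cohort. A single carrier of an uncommon characteristic among the cases can then be enough for significance. For other prevalences, no possible result is significant.

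At stake is which characteristics the study reports as affecting HIV acquisition on cabotegravir, and which enter any multivariable model. Results go into annual interim reports, regulatory reports and publications (section 11.2). The direction of the error changes with the prevalence of the characteristic, so a reader cannot correct for it by eye. The protocol already uses exact methods for the same rare events in Table 1, so an uncorrected large-sample test on those counts does not fit with its own planning.

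**Working it through.** **1. The plan's own figures.** Clopper-Pearson limits are the 2.5% quantile of Beta(x, n−x+1) and the 97.5% quantile of Beta(x+1, n−x). For n = 500 and 1.00% (x = 5) they are 0.3255% and 2.3181%, as printed in Table 1. All 18 rows of Table 1 and all 5 rows of Table 2 reproduce, apart from one last-digit rounding (0.0119 against 0.0118).

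**2. Expected cases** = people × years × rate.
- Minimum design: 500 × 3 × 0.20/100 = 3.0, and 500 × 3 × 0.40/100 = 6.0.
- Upper bound, all 500 followed for five full years: 500 × 5 × 0.20/100 = 5.0, and 500 × 5 × 0.40/100 = 10.0.
- Table 1 at N = 500: 0.25% to 2.5% of 500 = 1.25 to 12.5.
- Three years at N = 1000: 6 to 12. Three years at N = 2000: 12 to 24.

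**3. Smallest expected cell.** With m cases among N people, K of whom have the characteristic, the smallest expected count is m × min(K, N−K)/N, which is at most m/2. For m = 3 to 6 that is at most 1.5 to 3.0. For m = 9 it is at most 4.5. It first reaches 5 at m = 10 with a 50% characteristic.

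**4. True size at an assumed two-sided 5%.** With margins fixed, the number of carriers among the cases is hypergeometric (N, K, m). The size is the sum of the probabilities of all tables with p < 0.05.

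Worked example with m = 3 and K = 25 (5% prevalence). If one of the three cases is a carrier, X² = 500 × (1×473 − 2×24)² / (3 × 497 × 25 × 475) = 5.10, so p = 0.024. Fisher's test gives p = 0.143 on the same table. The chance of at least one carrier is 1 − (475×474×473)/(500×499×498) = 14.3%, and that is the true size of the Pearson test.

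Results in percent, N = 500:

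| Prevalence | 2% | 3% | 5% | 10% | 20% | 30% | 40% | 50% |
|---|---|---|---|---|---|---|---|---|
| 3 cases, Pearson | 5.89 | 8.75 | 14.29 | 2.76 | 10.34 | 2.66 | 6.34 | 0.00 |
| 3 cases, Fisher | 0.11 | 0.25 | 0.70 | 2.76 | 0.78 | 2.66 | 0.00 | 0.00 |
| 6 cases, Pearson | 11.47 | 16.78 | 3.18 | 1.52 | 1.63 | 6.93 | 8.58 | 3.03 |
| 6 cases, Fisher | 0.52 | 1.18 | 3.18 | 1.52 | 1.63 | 1.05 | 4.00 | 3.03 |

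For 3 to 6 cases at these eight prevalences, Pearson runs from 0% to 16.8%, Yates-corrected chi-square from 0% to 3.2%, and Fisher from 0% to 4.0%. Running the same enumeration over every K from 10 to 250 gives maxima of 17.0% for Pearson, 4.5% for Yates and just under 5% for Fisher, which cannot exceed 5% by construction.

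A six-category chi-square with assumed shares of 40, 20, 15, 10, 10 and 5% had a simulated size of 7.7% with 3 cases and 7.4% with 6.

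**5. Continuous variables.** Simulated with 3, 4 or 6 cases against the rest, the pooled t-test rejected in 4.5% to 5.3% of runs for normal data and 4.3% to 4.8% for skewed data. Wilcoxon rejected in 3.9% to 4.9%.

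**The case against.** **The test may be run with a continuity correction.** The protocol says only chi-square. With Yates' correction the size does not exceed 5%, so the inflation is not certain. This stands as a limit on the size of the problem. It is also a reason to name the test, since the wording permits a version that fails.

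**The count is a scenario.** It assumes 500 people, 3 years and pivotal-trial rates. At 12 cases and the same prevalences, uncorrected Pearson does not exceed 5.0%. This stands, and the range must be given. The count can also fall, through discontinuation, through counting only infections in people adhering to the regimen, or at the 12- and 24-month interim reports.

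**Little depends on it.** No formal hypothesis is tested, no significance level is stated, the primary effectiveness measure is a proportion, and the models are conditional on feasibility. With 3 to 6 events they would probably not be fitted. This limits the impact but leaves the univariate comparison, which is unconditional.

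**A small-cell rule belongs in the analysis plan.** That would answer a missing detail. Here the protocol itself names the test and the selection rule.

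**Stronger readings that are not supported.** A reader might infer that the t-test is equally unreliable. Step 5 shows that it is not. A Welch t-test on skewed data would be off (12% to 19%), but the protocol sends non-normal variables to Wilcoxon. A reader might also infer that the chi-square test always produces too many false positives. It does not: with 6 cases and 5%, 10%, 20% or 50% prevalence it is conservative and has the same size as Fisher's test.

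**Conclusion.** The point holds for the chi-square test and for the selection of covariates on its result. With 3 to 6 cases among 500, an uncorrected Pearson test at a nominal 5% has a true size of 0% to about 17%, governed by the prevalence of the characteristic. This rests on four assumptions: a 5% level, no continuity correction, 500 participants with full three-year follow-up, and pivotal-trial incidence. The small-cell problem persists in every 2x2 table up to 9 cases at N = 500 and eases as the count grows. It does not extend to the t-test or Wilcoxon rule, and it does not touch the primary effectiveness proportion. It is a modest correction to a secondary comparison in a descriptive study.

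**What to change.** In the Objective 3 comparison in section 7.6.1:
- Replace the chi-square test by Fisher's exact test, or its exact extension where there are more than two categories.
- Report exact confidence intervals with each comparison.
- Delete the rule that selects covariates on univariate significance.
- Leave the t-test and Wilcoxon rule as it is.

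The last deletion matters as much as the test: an exact test will not make a multivariable model supportable on 3 to 6 events. The cost is a sentence or two and standard software, with no extra data. The downside is that Fisher's test is conservative, with a true size of 0% to 4.0% in the scenarios above, so real associations will be hard to detect. With this few cases that is largely unavoidable, and the exact intervals will show it.

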- b) Individuals with undiagnosed prevalent infections at the time of CAB PrEP initiation
- c) Durability of INSTI-based vs. non-INSTI based regimens (e.g., the numbers and proportions of those who achieve and maintain virologic suppression, the time to virologic suppression, the time to virologic breakthrough), as well as any INSTI resistance-associated substitutions that are detected upon ART failure

5) Adherence and Durability

- a) Adherence to CAB LA PrEP including OLI will be estimated from data collected via health record data
- b) Non-adherence to the dosing schedule will be assessed by:
 - Estimating the number of individuals that missed one or more consecutive injections without taking daily oral PrEP bridging while not on CAB LA injections and mean and median number of injections missed during a 6 and a 12-month period
 - Estimating the number of individuals who received the injections seven or more days later than their scheduled injection visit and median duration of delayed injections
 - Estimating the number of individuals who missed one or more consecutive injections without taking daily oral PrEP bridging or those who received the injections seven or more days later than their scheduled injection visit (Combined group a OR b) and describe characteristics for the individuals that are nonadherent
- c) Discontinuation will be defined as 2 injection cycles (~127 consecutive days) in which no injections were administered without oral PrEP bridging
- d) Describe the frequency and the regimen used for oral PrEP bridging to cover planned delayed or missed injections
- 6) Frequency of resistance to INSTIs and specific mutations among the following groups:
 - a) CAB LA PrEP started when the individual had undiagnosed HIV and subsequent emergence of resistance while on CAB monotherapy
 - b) CAB LA PrEP discontinued
 - without subsequent oral PrEP & potential risk of HIV acquistion and viral resistance during CAB LA PK tail
 - switched to oral PrEP and acquire HIV during the follow-up period and develop resistance during subsequent follow-up period while on treatment with ARVs
 - c) Incident HIV diagnosis while adhering to CAB LA for PrEP and development of resistance during treatment for HIV
- 7) Frequency of DILI and HSRs following CAB OLI and CAB LA injections assessed at 6, 12, 24, 36, and >36 months.

Hepatotoxicity related to administration of CAB for PrEP (i.e., DILI) as described below will be tabulated:

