Analysis for Objective 2 (Monitor for adherence by assessing the frequency of delayed and missed injections without oral PrEP bridging)

Adherence will be estimated using the dates of injections. Proportion and number of individuals with ≥ 1 delayed (≥ 7 days)and/or ≥ 1 missed injection without oral PrEP bridging over 6, 12, 24, 36, >36-month periods will be provided. Additionally, mean (median) number of delayed and missed injections will be provided for each period. Proportion and number of individuals with ≥ 7 days delay of CAB LA PrEP injection over 6, 12, 24, 36, >36-month periods will be provided. Additionally, mean (median) number of days delayed will be provided for each period.

Characteristics of persons with delayed or missed injections without oral PrEP bridging will be compared with those that are on time with the injections for 6, 12, 24, 36, and >36-month periods using t-test for continuous variables (Wilcoxon rank sum test for not normally distributed variables) or chi-square test for categorical variables.

Proportion and number of individuals who discontinue CAB LA PrEP over 6, 12, 24, 36, and >36-month-periods and overall will be provided. Additionally, distribution of individuals who discontinued by most common discontinuation reasons will be provided and will be used to understand whether individuals are missing injections or choosing to discontinue the regimen. Characteristics of persons who discontinue vs persons who stay on therapy will be compared for 6, 12, 24, 36, and >36-month periods using t-test for continuous variables (Wilcoxon rank sum test for not normally distributed variables) or chi-square test for categorical variables.

If feasible, risk of delayed or missed injections and separately risk of discontinuation will be assessed using negative binomial model with log-link function accounting for sex, age group, race/ethnicity, and other characteristics found significant in univariate analysis.

Analysis for Objective 3 (Effectiveness: Monitor for incidence of HIV diagnoses while on CAB for PrEP)

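### A negative binomial model is named for yes/no outcomes: it overstates standard errors for discontinuation, while for HIV the real weakness is covariate screening on a handful of cases

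*Protocol*

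**What the plan says.** Protocol section 7.6.1 names the negative binomial model in two places.

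- **Objective 3 (HIV).** Risk of HIV acquisition is to be modelled with a "negative binomial model with log-link function with binary outcome (HIV diagnosis vs not) if feasible". Covariates come from univariate testing: "Participant characteristics significantly impacting acquisition of HIV based on univariate analysis will be selected for multivariable analysis". For categorical variables the only test named is chi-square.
- **Objective 2 (adherence and discontinuation).** Again if feasible, "risk of delayed or missed injections and separately risk of discontinuation will be assessed using negative binomial model with log-link function". The text does not say whether the delayed or missed outcome is a count or a yes/no variable. The same section summarises it both ways: as the proportion with at least one event, and as a number ("mean (median) number of delayed and missed injections will be provided for each period").

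Discontinuation is a state that a person either reaches or does not. Section 7.3.2 reads: "Discontinuation will be defined as 2 injection cycles (~127 consecutive days) in which no injections were administered without oral PrEP bridging".

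On size, section 7.4.1 states: "The study aims to include a target of at least 500 participants initiating CAB LA for PrEP". Table 1 considers incident HIV of 0.25% to 2.5%, and Table 2 considers discontinuation of 2.5% to 20%. No formal hypothesis is tested.

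**The concern.** The negative binomial is a distribution for counts that vary more than a Poisson count. A 0/1 outcome with probability p has variance p(1-p), which is always below the Poisson variance p. The extra dispersion parameter therefore has nothing to estimate and runs to its lower boundary. The standard errors reported by the model are then those of a Poisson model, or larger, and exceed the true ones. Confidence intervals for predictors of discontinuation would be too wide. Describing who discontinues and who is non-adherent is a stated objective (section 6, objective 2).

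For HIV there is a second and different problem. Very few cases are expected, yet covariates for the multivariable model are to be chosen by univariate significance, using a large-sample test in tables with tiny cells. Predictors of HIV on cabotegravir PrEP could be reported that reflect one or two chance coincidences.

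**Working it through.** **1. The plan's own figures.** Clopper-Pearson limits from beta quantiles with x = N × p reproduce Tables 1 and 2. For example, N = 500 with discontinuation of 20% gives 0.1658 to 0.2378, and HIV of 1.00% gives 0.3255% to 2.3181%. The design tables are sound, and their ranges are used below.

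**2. Standard-error excess for a log-link model on a 0/1 outcome.** The true variance is p(1-p).

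- Dispersion estimated, so at its zero boundary: working variance p, ratio of standard errors 1/√(1-p).
- Dispersion fixed at 1, as an assumption about software that the protocol does not state: working variance p + p², ratio √((1+p)/(1-p)).

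| Outcome | p | Dispersion estimated | Dispersion fixed at 1 |
|---|---|---|---|
| HIV (Table 1) | 0.25% | +0.1% | +0.3% |
| HIV | 2.5% | +1.3% | +2.5% |
| Discontinuation (Table 2) | 2.5% | +1.3% | +2.5% |
| Discontinuation | 5% | +2.6% | +5.1% |
| Discontinuation | 10% | +5.4% | +10.6% |
| Discontinuation | 15% | +8.5% | +16.3% |
| Discontinuation | 20% | +11.8% | +22.5% |

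With 250 per group and 20% in both, the standard error of the log risk ratio is √(2/50) = 0.200 under the model, against a true √(2 × 0.8/50) = 0.179. In 20,000 simulated data sets the nominal 5% test rejected in 2.8%, against 4.9% with robust variance. In trial negative binomial fits at 2%, 10% and 20% (Python statsmodels), the dispersion estimate was usually close to zero and no standard errors were returned.

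**3. Power for discontinuation.** The contrast is an assumption: 20% versus 30%, 250 per group, log(1.5) = 0.405.

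- True SE = √(0.8/50 + 0.7/75) = 0.159.
- Model SE, dispersion zero = √(1/50 + 1/75) = 0.183.
- Correct analysis: Φ((0.405 - 1.96 × 0.159)/0.159) ≈ 0.72.
- Negative binomial: Φ((0.405 - 1.96 × 0.183)/0.159) ≈ 0.62, or about 0.52 with dispersion fixed at 1.

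Simulation gives 0.73, 0.62 and 0.52. This contrast averages 25%, a little above Table 2. With 16% versus 24%, which averages 20%, the formula gives 0.60 against 0.51.

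**4. HIV: the model family hardly matters.** For an assumed 2% versus 5%, simulated power is 0.39 with either model. With 1% in both groups (5 events expected), 16% of simulated data sets had no event in one group, so none of these models could give a risk ratio.

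**5. HIV: expected cases and screening.** Section 5.1 gives 0.20 and 0.40 per 100 person-years on cabotegravir in the two pivotal trials. Assuming 500 people with 3 years each (1,500 person-years), that is 3 to 6 cases. Table 1's range at N = 500 gives 1.25 to 12.5.

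As an illustration, take 3 cases and a trait held by 25 of 500 that is unrelated to HIV.

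- One case with the trait already gives an uncorrected chi-square of 500 × (1 × 473 - 2 × 24)² / (3 × 497 × 25 × 475) = 5.1, above 3.84.
- P(at least one case has the trait) = 1 - (475 × 474 × 473)/(500 × 499 × 498) = 14.3%. That is the actual size of the nominal 5% test.
- Fisher's test rejects only with two or three such cases: (300 × 475 + 2,300)/20,708,500 = 0.7%.

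**The case against.** The strongest reply is that little depends on these models. No formal hypothesis is tested and no power is claimed. Both negative binomial models are to be fitted only if feasible. The primary effectiveness measure is a proportion, and section 7.4.1 shows the "precision of the estimates of the proportion with incident HIV, using Exact Clopper Pearson confidence limits under different scenarios". Offsets, dispersion handling, robust variance and small-cell fallbacks are commonly left to the statistical analysis plan, which is not at hand. The error is also conservative, so it cannot itself create false predictors. All of this stands and limits the weight of the point. It does not make the family suitable: the protocol itself pairs a count model with an outcome that it calls binary, and intervals that are too wide are wrong in a descriptive study as well.

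Three stronger readings are tempting, and the document does not support them.

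- *That the model spoils the HIV analysis.* The binary wording appears there, but at Table 1's rates the standard-error excess is at most 1.3% (2.5% with dispersion fixed at 1).
- *That standard errors are 40% or more too large.* That needs an outcome near 50%. The any-versus-none non-adherence outcome in section 7.3.2 could be common, but the protocol gives no figure for it.
- *That the negative binomial is wrong for delayed or missed injections.* Section 7.6.1 may mean the number per person, for which it is a reasonable choice.

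The 14% test size belongs to one chosen configuration. It shows that screening is unreliable here, not that every selected predictor would be false.

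**Conclusion.** The point holds, at modest weight. For discontinuation the named family is wrong and the cost is measurable: standard errors 1.3% to 11.8% too large over Table 2 (2.5% to 22.5% if dispersion is fixed at 1). At the upper end this costs about 10 percentage points of power under an assumed risk ratio of 1.5 with equal groups of 250. The same criticism applies to delayed or missed injections only if they are modelled as any versus none.

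For HIV the family is also wrong in principle but numerically harmless. The defect that matters is covariate selection by univariate chi-square on about 3 to 6 cases. That count assumes pivotal-trial rates and 3 years on treatment for all 500 people.

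The missing offset is no finding without the analysis plan. The primary effectiveness proportion and Tables 1 and 2 are unaffected.

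**What to change.** Amend the model wording in section 7.6.1:

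- **Discontinuation, and any-versus-none delayed or missed injection:** Poisson regression with robust (sandwich) variance, or log-binomial regression.
- **Number of delayed or missed injections:** keep the negative binomial, and say that the outcome is a count.
- **HIV:** Fisher's exact test for categorical comparisons. Drop selection by univariate significance. Replace the negative binomial by a Firth-penalised or exact model with one pre-named covariate at a time.

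The cost is about one paragraph of analysis text, with no change to data collection or sample size. Exact and penalised methods are slightly conservative with few events, and adjusting for one covariate at a time gives up a joint model that the expected case count could not support.
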